Functional magnetic resonance imaging (fMRI) studies by our team converge on the central role of working memory in smoking relapse. We showed that brief (e.g., 24 hr.) abstinence from smoking produces working memory deficits that are associated with reduced neural activity in cognitive control circuits and weakened resting state functional connectivity [25-29]. These altered brain responses may compromise cognitive resources needed to resist urges to smoke, thereby contributing to relapse [26, 30]. While working memory is one mechanism underlying relapse, additional neurobehavioral pathways are clearly important [31]. For example, neural reactivity to smoking cues also increases risk of relapse [31, 32]. Further, psychological stress can enhance neural responses to smoking cues [33, 34] and increase smoking intensity [35, 36]. Stress can also impair working memory [37]. The proposed study, to our knowledge, will be the first prospective study to examine the contributions of resting BOLD and BOLD signal change during working memory, cue reactivity, and psychological stress to subsequent smoking relapse. We will determine whether these mechanisms contribute to relapse beyond subjective and behavioral assessments, and explore the interactions among these processes.

Using our validated fMRI abstinence challenge paradigm [25, 27-30], 200 smokers will complete two 1-hour pre-treatment fMRI scans: after smoking satiety and after 24 hours of confirmed abstinence. We will examine neural responses during performance of tasks probing working memory, cue reactivity, and stress response as well as resting state functional connectivity. Participants will then set a target quit date, receive smoking cessation counseling, and be monitored for 6 months to assess time (days) to relapse, using a validated smoking relapse protocol [30, 38]. The primary outcome is time to relapse. Secondary outcomes include abstinence symptoms and smoking status at 30 days.

OBJECTIVES

1. Overall Objectives - (Main Study)

Aim 1: To identify brain mechanisms that increase vulnerability to relapse, using a pre-treatment abstinence challenge paradigm.

Hypothesis: *Altered Blood Oxygen Level Dependent (BOLD) signal during 24-hr abstinence challenge (vs. smoking satiety) will increase the risk of faster relapse during a subsequent quit attempt.*

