Data Screening: Prior to performing analyses, standard data screening/cleaning procedures will be applied. These procedures will (a) screen the data for data-entry errors, (b) check for outliers, (c) assess the extent and pattern of missing data, (d) create all summary scores needed for analysis, and (e) check that appropriate distributional assumptions are met. Assumptions will be examined using standardized residuals, influence diagnostics, and graphical displays. We will employ image quality assessment procedures to examine global and ROI-based raw and processed temporal signal-to-noise ratio, absolute and relative motion, and signal spike count. Subjects with potential outliers (>2 SDs above mean) will be flagged to determine if the time-series is valid, and if so it will remain. Otherwise it will be corrected or removed from the analysis. The final sample will be examined in a similar fashion to determine whether any subjects warrant data cleaning or exclusion from the final analysis. All analyses will be conducted using Stata software (STATA Corporation, College Station, Texas).

Missing Values: We will examine the characteristics of those subjects who drop out to identify any associations between dropout and baseline measures. These analyses will be descriptive, as we expect few dropouts. Items missing at random on survey measures will be imputed prior to calculating final scores using conditional means, estimated with a version of Buck’s method [65]. The analyses will also be repeated using only complete observations to assure that parameter estimates are not impacted by imputation.

Task fMRI: fMRI preprocessing will use standard algorithms in FSL (FMRIB’s Software Library, www.fmrib.ox.ac.uk/fsl) including distortion correction, slice-time correction, motion correction, spatial smoothing, high-pass filtering (120s) and co-registration to the MPRAGE. fMRI preprocessing will also include removal of physiological noise related to in-scanner pulse and respiration measures using RETROICOR. After preprocessing, basic subject-level BOLD time series analysis will be carried out using the general linear model (GLM) in FSL, using a canonical double-gamma hemodynamic response function (HRF) for convolution, and linear contrasts to estimate task-specific BOLD responses for each individual. Temporal derivative and extended motion parameters will be included in models when appropriate. For the block-design

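### The image-quality flag points the wrong way for temporal SNR: it picks out high values and gives low values no trigger

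*Combined protocol and SAP*

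**What the plan says.** The Data Screening paragraph (Statistical Analysis) lists the image-quality measures as "global and ROI-based raw and processed temporal signal-to-noise ratio, absolute and relative motion, and signal spike count". The next sentence gives the trigger: "Subjects with potential outliers (>2 SDs above mean) will be flagged to determine if the time-series is valid". A series found valid stays in. A series that fails the validity check is dealt with as follows: "Otherwise it will be corrected or removed from the analysis". A second look is then promised: "The final sample will be examined in a similar fashion to determine whether any subjects warrant data cleaning or exclusion from the final analysis".

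The same paragraph opens with general cleaning steps, among them "b) check for outliers", which has no threshold or direction. It also mentions residuals, influence diagnostics and plots for checking model assumptions.

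The data screened here feed Aim 1. Under Modeling of Days to Relapse, the Cox predictors are ROI difference scores between the abstinent and the smoking session.

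**The concern.** One upper-tail rule follows a list of measures that do not share an adverse direction. Large motion or many spikes mean poor data. A large tSNR means good data. Read as written, the tSNR criterion selects the best data for a validity check and passes over the worst.

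The flag is the stated route to validity review, correction and removal. A series with low tSNR but unremarkable motion and spike count (local signal loss, for example) therefore has no image-quality trigger. Because each Aim 1 predictor is a difference between two sessions, one poor session is enough to degrade a participant's value. Random error in a predictor generally pulls its Cox coefficient towards zero.

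**Working it through.** The plan gives no expected number of flags, so there is no figure to reproduce. The check is a reading of the rule against each metric, followed by illustrative counts.

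**1. Rule against metric.** The plan does not define tSNR. The usual sense is assumed: mean signal divided by its standard deviation over time, so higher is better.

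| Metric | Poor quality lies | Rule flags | Match |
|---|---|---|---|
| Absolute motion | high | high | yes |
| Relative motion | high | high | yes |
| Spike count | high | high | yes |
| tSNR (global and ROI-based, raw and processed) | low | high | no |

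**2. Any other rule.** No other section of the document gives a lower-tail or two-sided threshold for tSNR. The second look at the final sample uses a similar approach and adds no direction of its own.

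**3. Illustrative size.** Inputs: threshold 2 SD (Data Screening); 200 participants with two sessions each (Background, Main Study: "200 smokers will complete two 1-hour pre-treatment fMRI scans: after smoking satiety and after 24 hours of confirmed abstinence"). Normality of tSNR is an assumption.

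- One tail: p = 1 − Φ(2) = 0.02275, about 2.3%.
- Per session: 200 × 0.02275 = 4.55, about 4.6 participants in the unflagged low tail of each tSNR measure. The same number is flagged in the high tail.
- Over both sessions: 400 × 0.02275 = 9.1 participant-sessions.
- A lower-tail rule would flag the same expected number (9.1), all in the poor tail. A two-sided rule would flag 2 × 0.02275 = 4.55%, or 400 × 0.0455 = 18.2.

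**4. Sensitivity to shape.** In 4,000 simulated samples of 200, using sample means and SDs:

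| Assumed tSNR distribution | Flagged (high tail) per 200 | Not flagged (low tail) per 200 |
|---|---|---|
| Normal | about 4.5 | about 4.5 |
| Left-skewed (reflected lognormal), sigma 0.3 | 0.3 | 8.1 |
| Left-skewed, sigma 0.5 | about 0 | 9.1 |
| Right-skewed (lognormal), sigma 0.3 | 8.1 | 0.3 |
| Right-skewed, sigma 0.5 | 9.1 | about 0 |

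The direction of the error does not depend on the distribution, but the count does.

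**5. What the motion criterion would catch.** In the same kind of simulation, with normal tSNR and lognormal motion (sigma 0.5), the share of low-tSNR participants also flagged on motion depends on how strongly low tSNR and high motion are linked:

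| Assumed latent correlation | 0 | 0.3 | 0.5 | 0.7 | 0.9 |
|---|---|---|---|---|---|
| Share caught by motion | 5% | 16% | 28% | 47% | 80% |

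The correlation is an assumption; the documents give none. Spike count was not simulated and could add to these shares.

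**The case against.** The strongest reply is that this is a drafting slip with little practical effect. It has four parts.

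- **The meaning can be inferred.** The rule seeks series that may be invalid, and its direction fits motion and spike count, the items named just before it. An analyst would probably use the adverse tail. That is plausible, but the text does not say so, and tSNR stands in the same list.
- **Other routes exist.** A reader might infer that the worst data are never reviewed. The documents do not support that. The team will examine all the quality measures, the general outlier step has no direction, and a poor series can be flagged on motion or spikes. The statement that low values are never flagged is true of the tSNR criterion alone. Still, none of these routes is a tSNR trigger, and the motion route may catch few or most of the cases.
- **Clean data are not thrown away.** A reader might infer that high-tSNR series could be removed. The rule keeps a series judged valid, and high tSNR is given nowhere as a ground for removal. The cost on that side is unneeded review. This part of the reply stands.
- **No effect on Aim 1 is shown.** A reader might infer a materially attenuated hazard ratio. The documents give no basis for a figure. As an illustration on assumed values, let 9 of 200 participants carry extra noise equal to the whole predictor variance. Mean variance becomes (191 × 1 + 9 × 2)/200 = 1.045, and the planned hazard ratio of 1.32 becomes exp(ln 1.32 / 1.045) = 1.30. The test statistic falls by a factor of 1/√1.045 = 0.978. Removing the nine costs about the same: √(191/200) = 0.977. Greater noise or several affected measures would change this, but neither can be set from the documents. This part also stands.

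The unit is uncertain too. The rule flags subjects and judges a time series, while Table 1 shows four functional runs per session. The counts above are per tSNR measure and per participant-session, and they should not be summed across correlated measures.

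**Conclusion.** The rule is wrong as written for one named metric. For tSNR it flags high values, which are the cleanest data, and sets no trigger for low values. This follows from the text and needs no distributional assumption.

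The harm is confined to a missing tSNR trigger for poor-quality data that enter the Aim 1 ROI difference scores. If tSNR is roughly normal, about 2.3% of values per measure, or about 4.6 of 200 participants per session, lie in the unflagged tail. Skew could move that from almost none to about 9 of 200. Some of these would be found by other checks, and the share is unknown. The effect on the hazard ratio cannot be worked out from the documents. The point justifies a correction to the screening rule and does not call the Aim 1 model into question.

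**What to change.** Replace the single direction in the Data Screening paragraph with one per metric:

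- flag tSNR (global and ROI-based, raw and processed) more than 2 SD **below** the mean;
- flag absolute motion, relative motion and spike count more than 2 SD **above** the mean;
- apply the same directions when the final sample is examined.

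The validity check and the keep, correct or remove steps can stay as they are. The cost is a change of about one sentence, with no new data and no change to the sample size or the Aim 1 model. Under normality the expected number of tSNR flags is the same as now, so the review load on that criterion does not grow.

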The proposed study is a prospective observational neuroimaging investigation utilizing a pre-treatment abstinence challenge and fMRI assessment to elucidate the mechanisms underlying smoking relapse. As shown in **Figure 1**, 200 eligible consenting smokers will be scanned on two separate occasions prior to the scheduled target quit date (week 4): once during smoking satiety and once after 24 hours of biochemically confirmed abstinence (order counterbalanced). The pre-treatment scans will both include a resting BOLD MRI scan and a BOLD fMRI scan while performing validated tasks probing working memory, cue reactivity, and stress reactivity. Participants will have an individual pre-quit counseling session (week 3), and will be counseled and monitored (with biochemical confirmation) for 6 months post target quit date, with the addition of a 12 month Follow-up survey completed remotely.

Recruitment & Retention Pilot

This pilot study will utilize a randomized controlled trial design to evaluate two components of behavioral economic strategies to improve recruitment and retention. To be eligible for the pilot study participants must meet all eligibility criteria for one of the four participating studies (828958, **824061**, 824860, 828125), have a phone capable of receiving SMS messages, and consent to receive SMS messages. ~576 participants will be enrolled across the four

[figure not shown]

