Key Exclusionary Criteria; Alcohol/Drugs). Participants who test positive for any exclusionary medications or recreational drugs will be deemed ineligible;

3. Self-administer a CLIA-waived urine pregnancy test (female participants of childbearing potential only). Participants who believe that they may be pregnant are instructed to discontinue participation at this time;
4. Perform a BrAC assessment to control for alcohol consumption. Participants with a BrAC greater than or equal to 0.01 at Intake Visit will be ineligible;
5. Participants will be asked to perform a CO breath assessment to verify smoking status. Participants with CO readings less than 8 parts per million (ppm) will be ineligible.
6. Complete a brief medical history form with a trained staff member; for female participants, this form will include brief questions regarding menstrual cycle phase and hormonal contraception use.
7. Complete Shipley Institute of Living Scale (SILS) IQ test. Participants earning less than an estimated WAIS-R IQ score of 85 will be ineligible;
8. Complete demographics and smoking history (smoking rate, nicotine dependence, age at smoking initiation, childhood adverse events) and paper and pencil questionnaires (craving, withdrawal, mood, intention to quit smoking, impulsivity and anxiety);
9. Complete the Magnet Safety Form and Emergency Contact Form as required for scheduling fMRI scans;
10. Provide a saliva sample for baseline Nicotine Metabolite Ratio (NMR) assessment.

Participants will be asked to refrain from using any study prohibited drugs (note – participants are allowed to take prescription medicines not in the exclusion list) throughout their participation in the study.

fMRI Scanning Sessions (Weeks 1 & 2). All participants will have two imaging sessions prior to their target quit date (week 1 & week 2). Both scan sessions will be identical except for the participant smoking status. One scan will be after 24 hours of abstinence (acceptable range = 18-30 hours) and the other after smoking as usual. Visits on scanning days can be scheduled at any time of day, as long as the second scan is within a 3-hour window +/- of the first scan. Including the 1hr fMRI scan, these visits are expected to be ~4hrs in duration.

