Following the fMRI scanning portion of the visit participants will provide another 3 salivary cortisol samples and complete the 2-item smoking urge questionnaire and stress rating 3 times in addition to a final set of questionnaires about mood, craving and withdrawal effects; immediately following the conclusion of the MIST, 15 minutes post-scan and 30 minutes post-scan. After the final salivary cortisol sample collection the session will end and participants will be free to leave.

fMRI Back-up Scheduling (week 1). Some participants may choose to be scheduled as a back-up for another participant's fMRI scan. This is done to ensure that this protocol is efficiently using the time that is reserved on the fMRI scanner. Participants who are scheduled as a back-up should prepare for their back-up scan visit in the same way that they would prepare for a primary scanning visit. On the day of the back-up, scan participants should arrive at the Center in the smoking state that they have been assigned to for their Scan 1. Upon arrival participants will go through the same visit check-in to verify eligibility for the visit.

If the primary participant for that day attends their visit and is eligible to proceed then the back-up participant will be compensated \$25 for their time and will be able to leave the center and will attend their Scan 1 visit as scheduled. If the primary participant for that day becomes ineligible for any reason or does not attend their visit the back-up participant will be promoted to primary and will continue on with the appointment as their scan 1. Participants who are promoted to primary will then be compensated as per the usual Scan 1 compensation plan.

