N-back task, analysis will focus on the parametric effect of increasing working memory load across four levels (linearly modeled [-3 -1 1 3]). For the cue reactivity task, the primary contrast will be smoking cues>neutral cues. For the stress task, the primary contrast will be stress > control blocks.

Subject-level statistical image maps will be transformed into a common anatomic space (Montreal Neurological Institute, MNI) for group-level analysis. Session (abstinence vs. smoking) whole brain, voxelwise analyses will test abstinence effects in brain regions specified above. The peak voxel in each significant cluster will be used to assign appropriate anatomical labels. Percent signal change within significant clusters will be utilized in regression models described below. Age, self-reported ethnicity, nicotine dependence severity (FTND), and withdrawal symptom severity will be included as covariates in the relevant statistical models. For all tests, significance will be determined using cluster $p < .05$ and voxel-height $Z > 2.33$.

Aim 1: Modeling of Days to Relapse:

The outcome associated with Aim 1 is censored time to event and the predictors are continuous measures (difference scores) extracted from ROIs associated with each neurobehavioral domain. We will test this hypothesis within each domain (working memory, cue reactivity, and stress) using Cox regression; the test statistic will be the z-score corresponding to the hazard ratio, with significance corrected for the total (8) cross domain ROIs. We will also test baseline clinical predictors and abstinence challenge-related performance measures (difference scores) for entry into each of the domain specific models.

Aim 2: Integrated Brain-Behavior Model:

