The levels of energy used to make magnetic resonance measurements are far less than are used in a single X-ray, and many patients have been safely studied using magnetic resonance techniques. However, some people become uncomfortable or claustrophobic while inside the magnet. If participants become uncomfortable, they may withdraw immediately from the fMRI portion of the study. During some of the MRI scans, participants have occasionally reported "tingling" or "twitching" sensations in their arms or legs, especially when their hands are clasped together. To prevent this, all participants will be instructed to keep arms and legs apart. The imaging component of this study is part of a research protocol, and is not intended to provide a comprehensive clinical fMRI examination of the brain. In the event that a significant brain abnormality is observed while processing subject brain images for the research study, the images will be reviewed by a radiologist. There will be no charge to the subject for this examination of their images. A report will be filed in the subject's chart at the Center. The subject will be contacted and Center staff will arrange for the radiologist's report and structural images to be sent to the subject and/or their physician. Subjects will also be offered a consult with the study physician. These possible finding(s) may or may not be significant and may lead to anxiety about the subject's condition and to further work-up by the subject's physician.

Assessments: The MIST task has the potential to induce mild stress; however, in our preliminary study of 40 participants no adverse psychological consequences were reported. Nonetheless, we will take several steps to minimize this risk after each scanning session. To maintain fidelity of the manipulation between repeated sessions, subjects will not be fully debriefed until after the second fMRI scan. However, on each scan day the research staff will assess the participant's current stress level immediately after the fMRI scan and just before they

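### Scan order is counterbalanced by design but is not named as a covariate in the Aim 1 models, whose predictors are between-session difference scores; adding it is a free improvement

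*Combined protocol and SAP*

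**What the plan says.** Under Study Design (2. Design, Main Study), participants are scanned "once during smoking satiety and once after 24 hours of biochemically confirmed abstinence (order counterbalanced"). Under fMRI Scanning Sessions, "Both scan sessions will be identical except for the participant smoking status". Order is set in advance: the back-up scheduling text has participants arrive "in the smoking state that they have been assigned to for their Scan 1".

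In the Aim 1 paragraph of the Statistical Analysis section, "the predictors are continuous measures (difference scores) extracted from ROIs associated with each neurobehavioral domain". The same paragraph will also test baseline clinical predictors and "abstinence challenge-related performance measures (difference scores) for entry into each of the domain specific models". The imaging analysis is described as "Session (abstinence vs. smoking) whole brain, voxelwise analyses will test abstinence effects in brain regions specified above". The covariate sentence is "Age, self-reported ethnicity, nicotine dependence severity (FTND), and withdrawal symptom severity will be included as covariates in the relevant statistical models".

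Counterbalancing of the scans is mentioned only in the Design section. No order, period or session-number term appears in the Aim 1 or Aim 2 Cox models or in the voxelwise session contrast. The fixed order described under Scanning Protocol is the order of tasks within a scan, which is a separate matter.

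**The concern.** Counterbalancing is enough when the target is a mean difference, because a first-to-second-scan change averages out over the two order groups. Aim 1 does not test a mean. It uses each person's abstinent-minus-satiety score as a predictor. If responses shift by p between first and second scan, the score carries +p for those scanned abstinent second and −p for those scanned abstinent first. The two groups then differ by 2p for a reason unrelated to abstinence.

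That added variance attenuates the hazard ratio on which each of the eight ROI tests rests, at alpha 0.0085. Some change on repetition is plausible because the same tasks are run twice. The protocol already guards against one such effect in the stress task: "To maintain fidelity of the manipulation between repeated sessions, subjects will not be fully debriefed until after the second fMRI scan". It does so by design, with no matching term in the analysis. Aim 1 is the primary hypothesis, and the factor needed to remove a common shift is already recorded for every participant.

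**Working it through.** **Inputs.** From Power and Sample Size Considerations: n = 200, alpha 0.0085, 80% power, one-sample effect size d = 0.25, hazard ratio (HR) 1.32. The documents do not give the number of relapses, the sidedness of the test, the unit of the HR, or the size of any order effect. I take the test as two-sided and the HR as per SD of the score. I treat the order-group gap g = 2p as an assumption and show 0.2, 0.4, 0.6 and 1.0 SD of the order-free score.

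**Reproducing the plan's figure.** With z(1 − 0.0085/2) = 2.632, z(0.80) = 0.842 and ln 1.32 = 0.2776:

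- Relapses needed = (2.632 + 0.842)² / 0.2776² = 156.5, so 157 of 200.
- One-sample t test, d = 0.25, n = 200: power 80.9% from the noncentral t.

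Both agree with the stated 80% on the two-sided reading. One-sided, the t test would give 86.9%.

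**Effect of leaving order out.** Write the observed score as the order-free score (SD 1) plus or minus p. Its variance is 1 + p², so the log HR per observed SD is divided by √(1 + p²). With D relapses:

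power = Φ(√D × 0.2776 / √(1 + p²) − 2.632)

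For g = 1.0, p = 0.5 and D = 157: √157 × 0.2776 / √1.25 = 3.111, and Φ(3.111 − 2.632) = 68.4%. With no gap: Φ(3.479 − 2.632) = 80.2%. The HR per unit of score is exp(0.2776 / (1 + p²)), and order's share of score variance is p² / (1 + p²). The one-sample column uses d = 0.25 / √(1 + p²).

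| Gap g (SD) | Order's share of variance | HR per unit | Power, D = 140 | Power, D = 157 | Power, D = 180 | One-sample power |
|---|---|---|---|---|---|---|
| 0 | 0% | 1.320 | 74.3% | 80.2% | 86.3% | 80.9% |
| 0.2 | 1.0% | 1.316 | 73.8% | 79.7% | 85.9% | 80.4% |
| 0.4 | 3.8% | 1.306 | 72.2% | 78.2% | 84.6% | 79.0% |
| 0.6 | 8.3% | 1.290 | 69.7% | 75.8% | 82.5% | 76.6% |
| 1.0 | 20.0% | 1.249 | 62.0% | 68.4% | 75.8% | 69.3% |

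With order in the model, each column returns to its first row.

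**The other reading.** If HR 1.32 is per SD of the score as observed, the stated 80% already includes any order noise. Adjustment then multiplies the standardised effect by √(1 + p²). At D = 157, power rises from 80.2% to 80.6%, 82.0%, 84.1% and 89.6% for the four gaps.

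**Simulation.** Cox models, n = 200, exactly 157 relapses, HR 1.32 per order-free SD, 4,000 runs, standard error about 0.7 point:

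| Gap g (SD) | Power without order | Power with order |
|---|---|---|
| 0 | 78.1% | 78.2% |
| 0.2 | 78.8% | 79.0% |
| 0.4 | 76.9% | 78.4% |
| 0.6 | 73.7% | 77.4% |
| 1.0 | 66.0% | 79.3% |

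Power is generally one to two points below the formula, but the pattern is the same, and the first row shows no cost when there is no order effect. Adding four independent covariates to both models leaves the comparison essentially unchanged (78.0% against 78.1% at g = 0; 65.8% against 77.8% at g = 1.0).

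**False positives.** If order has no effect on relapse, omitting it does not inflate type I error: simulated 0.0087 without the term and 0.0077 with it, at g = 1.0 and nominal 0.0085. If order itself affected relapse with an assumed HR of 1.2 or 1.5, the unadjusted rate would be 0.018 or 0.058, against 0.010 or 0.009 adjusted. The documents neither state nor exclude such an effect.

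**The case against.** The strongest reply is that the text does not settle the omission and the gain may be small.

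- **The list may not be closed.** The covariate sentence refers loosely to relevant models, and the Aim 1 paragraph gives no fixed covariate list. The Measures section says estradiol and testosterone will be used to control for between-session differences, yet neither hormone is in that sentence. Order adjustment may therefore already be intended. This stands, and in that case the fix only records the intention.
- **The design limits the shift.** Each ROI score is a within-session contrast (memory load, smoking against neutral cues, stress against control), so a general signal change between scans cancels. Participants practise before each scan, and the second scan is held within 3 hours of the first one's time of day. This makes a large shift less likely. It does not exclude habituation or learning that alters the contrast itself.
- **The loss is assumed.** At gaps of 0.2 and 0.4 SD it is 0.5 and 2.0 points. A loss above 10 points needs order to explain about a fifth of the score variance, which nothing in the documents supports.
- **The planned effect may already contain order noise.** The power section sets d = 0.25 beside effects observed in a prior study. On that reading the plan loses nothing against its stated 80%. It still forgoes a gain.
- **A fixed term removes only a uniform shift.** Practice effects that differ between people remain in the score. This is correct.

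These points bear on the size of the benefit. None shows a cost to adding the term or a reason to leave a design factor out.

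**Conclusion.** The point holds as a free improvement, not as an error: no stated figure is wrong because of it. That order is absent from the analysis section is certain; the size of the benefit is not. It rests on an assumed uniform first-to-second-scan shift, about 157 relapses inferred from the plan's own 80%, and an HR expressed per SD. Under those assumptions, omission costs 2 points of power or less for gaps up to 0.4 SD and about 12 points at 1.0 SD (80.2% to 68.4%). On the observed-SD reading the same gaps represent a gain forgone of up to 9.4 points (80.2% to 89.6%). Both readings favour adjustment, and the cost when there is no shift was not detectable.

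**What to change.** Add one sentence after the covariate list under Task fMRI: *Scan order (abstinent first or satiety first) will be a fixed covariate in every model that uses a between-session difference score.* This covers the Aim 1 and Aim 2 Cox models and the performance difference scores tested for entry. Include order in the voxelwise session contrast as well, coded +1/−1 so that the mean contrast keeps its meaning. Report the order split among analysed participants, because exclusions at either scan can upset the balance set at assignment.

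The cost is one sentence and one degree of freedom per model. No new data are needed, since order is assigned before Scan 1.
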